4.4 Patient Registration/Randomization Procedures

The Oncology Patient Enrollment Network (OPEN) is a web-based registration system available on a 24/7 basis. OPEN is integrated with CTSU regulatory and roster data and with the LPOs registration/randomization systems or the Theradex Interactive Web Response System (IWRS) for

retrieval of patient registration/randomization assignment. OPEN will populate the patient enrollment data in NCI's clinical data management system, Medidata Rave.

Requirements for OPEN access:

- A valid CTEP-IAM account;
- To perform enrollments or request slot reservations: Must be on an LPO roster, ETCTN Corresponding roster, or participating organization roster with the role of Registrar. Registrars must hold a minimum of an Associate Plus (AP) registration type;
- If a Delegation of Tasks Log (DTL) is required for the study, the registrars must hold the OPEN Registrar task on the DTL for the site; and
- Have an approved site registration for the protocol prior to patient enrollment.

To assign an Investigator (IVR) or Non-Physician Investigator (NPIVR) as the treating, crediting, consenting, drug shipment (IVR only), or receiving investigator for a patient transfer in OPEN, the IVR or NPIVR must list the IRB number used on the site's IRB approval on their Form FDA 1572 in RCR. If a DTL is required for the study, the IVR or NPIVR must be assigned the appropriate OPEN-related tasks on the DTL.

Prior to accessing OPEN, site staff should verify the following:

- Patient has met all eligibility criteria within the protocol stated timeframes; and
- All patients have signed an appropriate consent form and HIPAA authorization form (if applicable).

Note: The OPEN system will provide the site with a printable confirmation of registration and treatment information. You may print this confirmation for your records.

Access OPEN at [REDACTED] or from the OPEN link on the CTSU members' website. Further instructional information is in the OPEN section of the CTSU website at [REDACTED] or [REDACTED]. For any additional questions, contact the CTSU Help Desk at [REDACTED].

To receive site reimbursement for specific tests and/or bio-specimen submissions, completion dates must be entered in the OPEN Funding screen post registration. Please refer to the protocol-specific funding page on the CTSU members' website for additional information. Timely entry of completion dates is recommended as this will trigger site reimbursement.

4.5 Registration to Correlative and Companion Studies

There is one substudy within Alliance A221505. This correlative science study **must be** offered to all patients enrolled on Alliance A221505 (although patients may opt to not participate). This substudy does not require separate IRB approval. The substudy included within Alliance A221505 is:

- Biological correlates of adverse radiation response in A221505, Alliance A221505-ST1 ([Section 13.1](#))

If a patient answers "yes" to "My samples and related information may be used for the additional study described above," Question #1 in the model consent, they have consented to participate in the substudy described in [Section 13.1](#). The patient should be registered to Alliance A221505-ST1 at the same time they are registered to the treatment trial (A221505). Samples should be submitted per [Section 6.2](#).

4.6 Stratification Factors and Treatment Assignments

The factors listed below will be used as stratification factors. After a patient has been registered, the values of the stratification factors will be recorded, and the patient will be assigned to either hypofractionated or standard radiation dosing using the Pocock and Simon dynamic allocation

procedure, which balances the marginal distributions of the stratification factors between the treatment groups (Pocock-Simon).

Patients will be stratified before randomization based on planned intent for:

- autologous (+/- implant) vs.
- implant only breast reconstruction.
- Patients will be stratified before randomization based on:
 - immediate reconstruction vs.
 - planned for delayed breast reconstruction (**includes patients who have had no reconstruction or only a temporary expander placed at time of randomization.**)
- ** Patients undergoing immediate reconstruction will already have completed reconstruction at the time of randomization.
- *** Patients who have a tissue expander placed at the time of mastectomy and then have a delayed final reconstruction will be classified as delayed for purposes of stratification and randomization.

5.0 STUDY CALENDAR

The pre-study testing intervals are guidelines only. Laboratory and clinical parameters during treatment are to be followed using individual institutional guidelines and the best clinical judgment of the responsible physician. It is expected that patients on this study will be cared for by physicians experienced in the treatment and supportive care of patients on this trial.

Pre-Study Testing Intervals

- To be completed ≤ 7 DAYS before registration: Pregnancy test,
- To be completed ≤ 28 DAYS before registration: history and physical.

	Prior to Registration	Before RT [¥]	At completion of RT [€]	2 to 8 weeks post RT	6, 12, 18 mos. post RT*	2 years post RT*	30 mos., 3,4 and 5 years post RT**	10 and 15 years post RT***
Tests & Observations								
H&P, Weight, PS	X	X (1)	X	X	X	X	X	
Height	X							
Mastectomy or reconstruction complications		X	X	X	X	X	X	
Recurrence (scan or clinical) Assessment					X	X	X	X
Adverse Events Assessment		A	A	A	A	A	A	
Clinical Lymphedema Assessment		B	B	B	B	B	B	
Cardiac and Brachial Plexopathy Events					C	C	C	C
Arm Circum. Measure (see §10.5)		X			X (2)	X		
Photographs for Cosmetic Assessment		D				X (4)		
Laboratory Studies								
Serum or Urine HCG	E							
Hemoglobin A1C	F							
Questionnaires								
Breast-Q Post-mastectomy		G						
Breast-Q Post-reconstruction		G				X	X (3)	
LBCQ		X			X (2)	X	X (3)	
BLE		H			X (2)	X	X (3)	
Economic Surveys		I	J	I	J			
EQ-5D-3L		X			X	X		
Was It Worth It Questionnaire						X		
Correlative Study (optional)	To be collected at baseline, see Sections 6.2 and 13.1							
Whole Blood								

¥ May be completed at any time following patient consent (before or after registration, but prior to treatment)

€ May be completed within 72 hours of last radiation treatment.

* +/- 6 weeks.

** For 30-month visit, +/- 6 weeks; for 3, 4, and 5-year visits, +/- 3 months

*** +/- 6 months. All follow up, including survival status, done after 5 years will be gathered by record review only.

A Assessment of side effects related to radiation therapy should be assessed according to the history and physical examination.

B To be assessed per the CTCAE criteria.

C Will be assessed by medical record review.

D Only for patients with final reconstruction completed before radiation.

E For women of childbearing potential. Must be done within 7 days prior to registration.

F For diabetic patients only, to be done ≤ 90 days before registration.

G Breast Q Post Mastectomy questionnaire; unless already reconstructed, then Breast-Q Post Reconstruction.

H Only for patients who have had reconstruction

I Prior to RT, patients will be given the Patient Health Care Diary and the Health Care Expense Questionnaire (Appendix VII) to be returned to the clinic at the 2 to 8 week visit (see Section 10.7).

J After completion of RT, the patient will be given the Patient Health Care Utilization Diary (Appendix VIII) and will be asked to return it at the 12-month visit (see Section 10.7).

1 Need not be repeated if done within the past 30 days

2 To be completed at 6 months only. (up to 18 months, whenever reconstruction is completed, for BLE)

3 To be completed at 5 years only.

4 +/- 2 months

6.0 DATA AND SPECIMEN SUBMISSION

6.1 Data Collection and Submission

6.1.1 Data submission schedule:

A Schedule of Forms is available on the Alliance study webpage, within the Case Report Forms section. The Schedule of Forms is also available on the CTSU site within the study-specific Education and Promotion folder, and is named Time & Events.

6.1.2 Medidata Rave

Medidata Rave is a clinical data management system being used for data collection for this trial/study. Access to the trial in Rave is controlled through the CTEP-IAM system and role assignments.

Requirements to access Rave via iMedidata:

- A valid CTEP-IAM account; and
- Assigned a Rave role on the LPO or PO roster at the enrolling site of: Rave CRA, Rave Read Only, Rave CRA (LabAdmin), Rave SLA, or Rave Investigator.

Rave role requirements:

- Rave CRA or Rave CRA (Lab Admin) role must have a minimum of an Associate Plus (AP) registration type;
- Rave Investigator role must be registered as a Non-Physician Investigator (NP-IVR) or Investigator (IVR); and
- Rave Read Only role must have at a minimum an Associates (A) registration type.

Refer to [REDACTED] for registration types and documentation required.

Upon initial site registration approval for the study in Regulatory Support System (RSS), all persons with Rave roles assigned on the appropriate roster will be sent a study invitation e-mail from iMedidata. To accept the invitation, site staff must log in to the Select Login [REDACTED] using their CTEP-IAM username and password, and click on the accept link in the upper right-corner of the iMedidata page. Site staff will not be able to access the study in Rave until all required Medidata and study specific trainings are completed. Trainings will be in the form of electronic learnings (eLearnings) and can be accessed by clicking on the link in the upper right pane of the iMedidata screen. If an eLearning is required and has not yet been taken, the link to the eLearning will appear under the study name in iMedidata instead of the Rave EDC link; once the successful completion of the eLearning has been recorded, access to the study in Rave will be granted, and a Rave EDC link will display under the study name.

Site staff who have not previously activated their iMedidata/Rave account at the time of initial site registration approval for the study in RSS will receive a separate invitation from iMedidata to activate their account. Account activation instructions are located on the CTSU website in the Data Management section under the Rave resource materials (Medidata Account Activation and Study Invitation Acceptance). Additional information on iMedidata/Rave is available on the CTSU members' website in the Data Management > Rave section at [REDACTED] or by contacting the CTSU Help Desk at [REDACTED]

Patient-completed questionnaire booklets for this study are to be ordered prior to the registration of any patients (see Section 4.4). Samples of questionnaire booklets are available in Appendices I-III for reference and IRB submission only. They are not to be used for patient completion. Booklets

must be given to patients to complete and patients should be instructed to return the booklets to site staff either in person or by mail and site staff will enter patient and caregiver responses into Rave.

The patient questionnaires for this study are only being made available in English for US participants.

CCTG institutions are to provide patient completed booklets translated into French to French speakers. The site is responsible for transcribing the patient responses from the French version into the English version, within Medidata Rave to submit to the Alliance Statistics and Data Center. The institution should retain the completed French version as source documentation.

6.1.3 Data Quality Portal:

The Data Quality Portal (DQP) provides a central location for site staff to manage unanswered queries and form delinquencies, monitor data quality and timeliness, generate reports, and review metrics.

The DQP is located on the CTSU members' website under Data Management. The Rave Home section displays a table providing summary counts of Total Delinquencies and Total Queries. DQP Queries, DQP Delinquent Forms and the DQP Reports modules are available to access details and reports of unanswered queries, delinquent forms, and timeliness reports. Review the DQP modules on a regular basis to manage specified queries and delinquent forms.

The DQP is accessible by site staff that are rostered to a site and have access to the CTSU website. Staff that have Rave study access can access the Rave study data using a direct link on the DQP.

To learn more about DQP use and access, click on the Help icon displayed on the Rave Home, DQP Queries, and DQP Delinquent Forms modules.

Note: Some Rave protocols may not have delinquent form details or reports specified on the DQP. A protocol must have the Calendar functionality implemented in Rave by the Lead Protocol Organization for delinquent form details and reports to be available on the DQP. Site staff should contact the LPO Data Manager for their protocol regarding questions about Rave Calendaring functionality.

6.1.4 Supporting Documentation

This study requires supporting documentation for pathology from mastectomy, clinical staging document at baseline, all operative notes, and any notes documenting complications or progression.

CPT Chart summary: To be completed at 12 months only. Summary of CPT billing codes from treating institutions in the U.S. from registration until 12 months after radiation.

6.2 Specimen collection and submission

All participating institutions must ask patients for their consent to participate in the correlative substudy planned for Alliance A221505-ST1, although patient participation is optional. Pharmacogenetic studies will be performed. Rationale and methods for the scientific components of these studies are described in [Section 14.0](#). For patients who consent to participate whole blood will be collected at the following time point for this study:

	Following registration and prior to RT*	Storage/ Shipping conditions	Submit to:
Whole blood (EDTA/lavender top) (see Section 6.2.2)	10 mL	pack/ship on cold pack over night	Alliance Biorepository at Mayo Clinic BAP

* Can be collected at any time, sites can schedule this blood draw to coincide with a standard of care blood draw

6.2.1 Specimen submission using the Alliance Biospecimen Management System

USE OF THE ALLIANCE BIOSPECIMEN MANAGEMENT SYSTEM (BioMS) IS MANDATORY AND ALL SPECIMENS MUST BE LOGGED AND SHIPPED VIA THIS SYSTEM.

BioMS is a web-based system for logging and tracking all biospecimens collected on Alliance trials. Authorized individuals may access BioMS at the following URL: [REDACTED] using most standard web browsers (Safari, Firefox, Internet Explorer). For information on using the BioMS system, please refer to the 'Help' links on the BioMS webpage to access the on-line user manual, FAQs, and training videos. To report technical problems, such as login issues or application errors, please contact: [REDACTED] For assistance in using the application or questions or problems related to specific specimen logging, please contact: [REDACTED]

After logging collected specimens in BioMS, the system will create a shipping manifest. This shipping manifest must be printed and placed in the shipment container with the specimens.

All submitted specimens must be labeled with the protocol number (A221505-ST1), Alliance patient number, patient's initials and date and type of specimen collected (e.g., serum, whole blood).

A copy of the Shipment Packing Slip produced by BioMS must be printed and placed in the shipment with the specimens.

Instructions for the collection of samples are included below. Please be sure to use a method of shipping that is secure and traceable. Extreme heat precautions should be taken when necessary.

Ship specimens on Monday through Friday only. Shipping by overnight service to assure receipt is encouraged. Do not ship specimens on Saturdays or the day before a holiday.

All specimens should be sent to the following address:

[REDACTED]
[REDACTED]
[REDACTED]
[REDACTED]
[REDACTED]

6.2.2 Whole blood collection, processing, and shipment

Whole blood collection: For patients who consent to participate, whole blood samples will be collected for the biomarker analyses described in [Section 13.1](#).

Collect 10 mL of peripheral venous blood in one or two lavender top tubes (K2EDTA anti-coagulant) at baseline (following registration and prior to radiation therapy).

Whole blood processing: The tube(s) should be inverted several times to mix the EDTA and refrigerated until shipped on cool pack by overnight mail to the Alliance Biorepository.

Label EDTA tubes with the following information:

- 1) Alliance study number (i.e., A221505)
- 2) Alliance patient number
- 3) Patient's initials (last, first, middle)
- 4) Procurement date and time
- 5) Whole blood

Shipping: The samples should be shipped the same day that the blood is drawn per Section 6.2.1.

6.3 Digital radiation therapy data submission using Transfer of Images and Data (TRIAD)

Transfer of Images and Data (TRIAD) is the American College of Radiology's (ACR) image exchange application. TRIAD provides sites participating in clinical trials a secure method to transmit images. TRIAD anonymizes and validates the images as they are transferred.

6.3.1 TRIAD Access Requirements

- A valid CTEP-IAM account.
- Registration and Credential Repository (RCR) registration type of: Associate (A), Associate Plus (AP), Non-Physician Investigator (NPIVR), or Investigator (IVR) registration type. Refer to the CTEP Registration Procedures section for instructions on how to request a CTEP-IAM account and complete registration in RCR.
- TRIAD Site User role on an NCTN or ETCTN roster.

All individuals on the Imaging and Radiation Oncology Core provider roster have access to TRIAD and may submit images for credentialing purposes, or for enrollments to which the provider is linked in OPEN.

6.3.2 TRIAD Installations

To submit images, the individual holding the TRIAD Site User role will need to install the TRIAD application on their workstation. TRIAD installation documentation is available at [REDACTED]

This process can be done in parallel to obtaining your CTEP-IAM account and RCR registration.

For questions, contact TRIAD Technical Support staff via email [REDACTED]

6.3.3 Procedures for Data Submission via TRIAD

Submission of treatment plans in digital format as DICOM RT is required. Digital data must include CT scans, structures, plan and dose files. This study uses TRIAD for RT data submission. Use of TRIAD requires several preliminary steps as described above. See [Section 4.2](#) for details. Additional information is available at: [REDACTED]

In the event that a site has not completed all steps required for TRIAD data submission in time to meet the timeline for on-treatment review, data submitted via SFTP will also be accepted. See the instructions for submission of data via SFTP on the IROC Rhode Island website under Digital Data.

See [Section 7.5](#) for items to be submitted for RT QA on-treatment review.

6.4 Submission of Photographs for Cosmetic Assessment

Photographs of both breast/reconstructed chest walls at the following time points will be submitted to IROC Rhode Island:

- Before radiation, only for patients with immediate reconstruction (only for those patients whose reconstruction is complete with final implants)
- 24 months after the completion of radiation for all patients

The photographs should be in an image format such as .jpg. Scanned photographs will not be accepted.

See [section 10.6](#) for instructions on taking the photograph.

The de-identified photographs should be submitted via email to [REDACTED]. Please put the protocol number and patient's study ID in the subject line of the email. Alternatively, photographs can be uploaded via TRIAD or submitted via sFTP. See 6.3.3 for instructions for submission via sFTP.

Questions regarding documentation should be directed to: [REDACTED]

7.0 TREATMENT PLAN/INTERVENTION

Radiation treatment may begin no sooner than 21 days after initial surgery or 21 days after the completion of adjuvant chemotherapy. Radiation therapy must begin no later than 84 days (12 weeks) after initial surgery or the completion of adjuvant chemotherapy, whichever is later.

- **Initial surgery** is defined as mastectomy and any subsequent surgeries related to the initial mastectomy, including additional margin resection, lymph node removal or immediate reconstruction. If neoadjuvant chemotherapy is used, then surgery must occur within 56 days after completing the cytotoxic component of therapy.
- **Chemotherapy** is defined as cytotoxic chemotherapy, not biological therapy, such as trastuzumab, pertuzumab, etc. Trastuzumab emtansine (Kadcyla) is classified as biological therapy for the purposes of this protocol and NOT chemotherapy.

Randomization: Patients will be randomized to either radiation in 25 fractions over 5-6 weeks or hypofractionation radiation in 16 fractions over 3-4 weeks. Radiation will be delivered to the chest wall/reconstructed breast and regional lymph nodes. The treating radiation oncologist must certify intent to treat regional lymphatics prior to registration.

7.1 Surgical Management

7.1.1 Mastectomy

Surgery may be completed as a total, simple, skin sparing, nipple sparing or modified radical mastectomy.

Margins should be negative, defined as no tumor on ink. A focally positive deep margin will be considered a negative margin if the deep margin is the pectoralis fascia and the pectoralis fascia was noted as removed in the operative description or pathology report. This is provided there is no evidence of pectoralis fascia invasion by imaging or pathological evaluation.

Lymph nodes must be evaluated by sentinel node biopsy or axillary dissection. The majority of these patients will have positive lymph nodes in order to qualify for enrollment. This protocol does not stipulate sentinel node versus axillary dissection, but does require lymph node management per standard of care. Patients will be recorded as having undergone a sentinel node only procedure or an axillary dissection. A sentinel node procedure will be considered an axillary dissection if more than 5 lymph nodes are removed.

Mastectomy and nodal evaluation must be completed within 56 days of the completion of neoadjuvant chemotherapy. Radiation must start per section 7.0.

7.1.2 Surgical Quality Assurance Requirements

There is no surgical credentialing required for participation in this trial. There is also no surgical quality assurance required for this trial.

Negative margins should be achieved prior to proceeding on to adjuvant radiation therapy. Negative margins are defined in section 7.1.1.

7.2 Breast Reconstruction

Reconstruction of the breast may occur before or after radiation but must be completed within 18 months of finishing radiation therapy, unless medically contraindicated.

A fluid filled tissue expander may be placed before or after radiation and maybe inflated or deflated for radiation. No change in volume of the expander may occur after radiation simulation and before the last fraction of PMRT. Air tissue expanders are not recommended and if utilized, must be deflated for radiation simulation and treatment delivery due to the difficulty with dose calculation and reporting at air/tissue interfaces. Additionally, the tissue expander is part of the radiation target volume, which must receive the prescription dose which is not possible in air.

Plastic surgeon may use any combination of allograft, saline, silicone, or autologous tissue flap for reconstruction. The method and timing of reconstruction must be documented on the eCRF.

Reconstruction intent must be stated at the time of registration, and may include the following:

- Implant only reconstruction before radiation
- Autologous reconstruction before radiation (with or without implant)
- Temporary expander placement at the time of mastectomy, radiation, with subsequent delayed reconstruction with implant only
- Temporary expander placement at the time of mastectomy, radiation, with subsequent delayed reconstruction with autologous tissue with or without implant
- Mastectomy without tissue expander, followed by radiation, with subsequent delayed reconstruction with implant, only.
- Mastectomy without tissue expander, followed by radiation with subsequent delayed reconstruction with autologous tissue with or without implant

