10.0 MEASUREMENT OF EFFECT**10.1 Ipsilateral Reconstruction Complications**

Reconstruction complications will be defined as:

- Capsular contracture (Baker Grade III or IV only)
- Complete failure of the implant/skin flap
- Unplanned admission for reconstruction related issue(s) including but not limited to infection, wound healing complication or pain
- Unplanned return to the operating room for recon related issue including but not limited to infection, prosthesis exposure, failed reconstruction, implant removal, wound healing complications or contracture management

Note: Complications related to the contralateral breast will be collected but will not count towards the assessment of the primary endpoint, ipsilateral breast complications will be counted towards the primary endpoint.

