11.3.2 Follow up for patients who do not complete radiation and breast reconstruction

Patients who complete radiation per protocol, but who do not complete reconstruction will also be followed as outlined in [Section 5.0](#) until disease recurrence, contralateral breast cancer, or a non-breast second primary cancer; or until an alternative treatment is given for up to 15 years

after the end of radiation therapy. All follow up (including survival) done after 5 years will be gathered by record review only.

Patients who experience disease recurrence, contralateral breast cancer, or a non-breast second primary cancer, or alternative treatment will discontinue protocol therapy and no further follow up will be required.

11.4 Managing Ineligible Patients and Registered Patients Who Never Receive Protocol Intervention

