12.2 Sample Size, Accrual Time and Study Duration

Our target sample size will be 792 evaluable patients (396 in each arm). To account for 10% drop-out due to cancellations or protocol deviations, our target accrual is 880 patients (440 per arm) (90% of 880 is 792).

The study design is a randomized, un-blinded, non-inferiority trial. It is assumed that the two-year breast reconstruction complication rate for the control arm (Arm 1: standard fractions) is 25%. Other assumptions for the sample size determination include:

- α (one-sided) = 0.025
- power = 90%
- non-inferiority margin: the absolute increase in the proportion of patients who experience
- a breast reconstruction complication within two-years is 10% above that of the control arm.
- one interim analysis (when 30% of the information is obtained) for futility

Under an alternative hypothesis that the true rates in the two arms are equal, a sample size of 792 (396 per arm) evaluable patients would give us 90% power to reject the null hypothesis of inferiority. The final analysis will take place after all patients have reached two years post-radiation. The anticipated accrual period is approximately 30 months, and the total study duration is approximately 60 months. We anticipate being able to accrue approximately 30 patients per month based on our best estimate extrapolated from recently closed intact breast trials looking at similar fractionations. It should be noted that if we instead assumed a complication rate of 50% in the control arm (the most statistically conservative, in terms of sample size), the above sample size would still give us approximately 80% power to reject the null hypothesis of inferiority (again with one-sided α of 0.025).

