Simulation studies of 10,000 clinical trials are conducted for the proposed group sequential design. The probabilities of early stopping (at the interim analysis) and empirical powers for various scenarios are summarized in the following table. Of particular interest, assuming that the two-year breast reconstruction complication rate is 25% for the control arm (Arm 1: conventional PMRT) and 35% for the hypofractionated PMRT (Arm 2), where the Arm 2 treatment is inferior to Arm 1, there is a 14.45% chance of stopping the trial early to conclude that hypofractionated PMRT is inferior. In another scenario where the complication rate of the conventional PMRT is 25% and that of hypofractionated is 25%, where the Arm 2 treatment is truly non-inferior to Arm 1, the likelihood of stopping early to conclude inferiority is 0.24% and the likelihood of the trial concluding that hypofractionated PMRT is non-inferior to conventional one is 90.84% (power).

Reconstruction complication rate		Interim analysis conclusion		Early stopping	Final analysis conclusion		Rejection (of H_0) rate
Conventional	Hypofractionated	Noninferior	Inferior		Noninferior	Inferior	
25%	35%	0.00%	14.45%	14.45%	2.37%	83.18%	2.37%
	30%	0.00%	2.86%	2.86%	34.51%	62.63%	34.51%
	25%	0.00%	0.24%	0.24%	90.84%	8.92%	90.84%

It should be noted that the primary analyses will be an intent-to-treat analysis where all patients randomized will be included in the analysis and will be analyzed based on the arm they were randomized to regardless of actual radiation schedule received. This analysis will not be stratified. Due to the random treatment assignment with stratification for the timing of reconstruction and type of reconstruction, it is expected that the baseline patient characteristics, including the planned reconstruction procedures, are roughly balanced across the two treatment arms. A sensitivity analysis stratified by timing and type of reconstruction surgery will be conducted.

The frequency and the proportion of patients who enrolled in the trial prior to reconstruction surgery who did not receive the surgery within 18 months of radiation as specified in the eligibility criteria will be summarized separately by arm. A secondary analysis excluding these patients will be conducted.

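### A planned reconstruction abandoned because of post-radiation chest-wall problems can count as a non-event in the primary analysis and is excluded from the secondary one, with no reason required

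*Combined protocol and SAP*

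**What the plan says.** All references are to the combined protocol and SAP.

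- **7.2** requires reconstruction but allows an exception: it "must be completed within 18 months of finishing radiation therapy, unless medically contraindicated". The cause of the contraindication is left open. Two of the six listed pathways involve no expander before radiation and two an expander only. Section 4.6 places all four in the delayed stratum. The eCRF must carry the method and timing of reconstruction; 7.2 does not ask why a planned one was not done.
- **10.1** defines the endpoint by four components: Baker III or IV contracture, "Complete failure of the implant/skin flap", unplanned reconstruction-related admission, and unplanned reconstruction-related return to the operating room. A failed reconstruction is named only as one reason for that return.
- **11.3.2** keeps unreconstructed patients under observation: "Patients who complete radiation per protocol, but who do not complete reconstruction will also be followed" on the study calendar, until recurrence, a new cancer or alternative treatment.
- **12.3.2** puts every randomized patient in the primary analysis. For patients enrolled before reconstruction and not reconstructed within 18 months, it gives the number and proportion by arm, and then: "A secondary analysis excluding these patients will be conducted".
- **12.6** deals with missing information, in terms of baseline characteristics and patient-reported outcomes. A patient followed to 24 months without reconstruction is not missing.

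**The concern.** Take a patient planned for delayed reconstruction without an expander. After radiation her skin or chest wall is judged unfit for surgery. She has no implant or flap to fail, and she may never have an unplanned admission or operation. She then enters the intent-to-treat denominator and not the numerator. The one analysis directed at patients like her removes her.

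The plan never states this scoring. It follows from the endpoint definition combined with the intent-to-treat rule. The primary objective (2.1) is whether the shorter schedule is non-inferior on reconstruction complications. If that schedule left more chest walls unreconstructable, neither planned analysis of the complication rate would count the excess, and both could move towards a non-inferiority claim.

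**Working it through.** **1. The plan's own figures.** Inputs from 12.2: "α (one-sided) = 0.025"; power 90%; control rate 25%; margin 10 percentage points; "Under an alternative hypothesis that the true rates in the two arms are equal".

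n per arm = (1.960 + 1.282)² × 2 × 0.25 × 0.75 / 0.10² = 394.1, so 395. The plan has 396, or 792 in total, and 792 / 0.90 = 880. At 396 per arm, power = Φ(0.10 / √(2 × 0.25 × 0.75 / 396) − 1.96) = Φ(0.10 / 0.0308 − 1.96) = 90.1%. Simulating the plan's test with its futility look (about 119 per arm) gave power 90.0% and type I error 2.46%, against 90.84% and 2.37% in 12.3.2. The design reproduces.

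**2. Set-up for the check.** Let true failure, with radiation-related abandonment counted as failure, be f₁ = 0.25 and f₂ = 0.35, exactly at the margin. Let a₁ and a₂ be the proportions abandoned for post-radiation ipsilateral problems with no other qualifying event. These are assumed; the documents give neither an abandonment rate nor the share of patients without an expander.

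- Intent-to-treat: p = f − a, with 396 per arm.
- Exclusion analysis: q = (f − a) / (1 − a), with 396(1 − a) per arm. For simplicity only these patients are removed; the plan would also remove those not reconstructed for other reasons.
- Probability of declaring non-inferiority = Φ[(rate₁ − rate₂ + 0.10) / SE − 1.96], with the unpooled SE of 12.3.2.

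**3. Worked case, 2% v 5%.**

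- Intent-to-treat rates are 0.23 and 0.30. SE = √((0.23 × 0.77 + 0.30 × 0.70) / 396) = 0.0313. Φ(0.03 / 0.0313 − 1.96) = 15.9%. Simulation with the futility look gives the same.
- Exclusion rates are 0.23 / 0.98 = 0.2347 and 0.30 / 0.95 = 0.3158, with 388.1 and 376.2 patients. SE = 0.0322. Φ(0.0189 / 0.0322 − 1.96) = 8.5%.

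**4. Range.** Chance of a false non-inferiority claim (nominal 2.5%):

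| Assumed abandonment, Arm 1 / Arm 2 | Intent-to-treat | Exclusion analysis |
|---|---|---|
| 0 / 0 | 2.5% | 2.5% |
| 3% / 3% | 2.5% | 2.0% |
| 5% / 5% | 2.5% | 1.7% |
| 2% / 4% | 9.3% | 5.5% |
| 2% / 5% | 15.9% | 8.5% |
| 3% / 8% | 37.4% | 17.9% |
| 5% / 2% | 0.17% | 0.27% |

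**5. Effect of counting these patients.** Scoring them as events restores 0.25 and 0.35, and the error returns to 2.5% in every row.

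**The case against.** Four points on the other side carry weight.

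- **Non-reconstruction is visible.** 12.3.2 reports its frequency by arm, so a marked imbalance would show. This stands. What the table cannot do, as specified, is separate radiation damage from patient choice or recurrence. The case report forms are not in the documents, so whether they already capture a reason cannot be judged; the plan text does not ask for one.
- **Chest-wall damage is measured elsewhere.** Fibrosis, chest wall pain, radiation dermatitis and wound complications are solicited adverse events (9.2.1), and acute and late radiation complications are compared between arms (12.4.1). This stands too: the trial is not blind to such damage. The gap is in the analyses of the reconstruction complication rate.
- **Many abandoned patients will already have an event.** A reader might infer that everyone whose reconstruction is abandoned is scored complication-free. The documents do not support that. The admission and re-operation components are open-ended, so an expander infection, exposure or removal that leads to an unplanned admission or operation counts. The gap is chiefly in the no-expander pathways, and in expander patients abandoned without a qualifying event.
- **The direction is not fixed.** A reader might infer that the scoring always favours non-inferiority. It does not, as the equal and reversed rows show.

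A reader might also argue that abandonment unrelated to radiation, equal in both arms, dilutes the difference and inflates the error. That is not relied on here. The null in 12.3.2 concerns the proportion among all patients in each arm, for which the error is nominal. The exclusion analysis already removes such dilution, and the fix below would not change it.

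**Conclusion.** The point holds in a limited, conditional form. An abandoned reconstruction with a post-radiation ipsilateral cause and no qualifying complication is, by implication, a non-event in the primary analysis and absent from the secondary one. No planned complication-rate analysis counts it as harm.

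The consequence depends on an imbalance that the documents do not quantify. With 2 to 5 points more such abandonment in the hypofractionated arm, and true failure at the margin, false non-inferiority is about 9% to 37% in intent-to-treat and 6% to 18% in the exclusion analysis. With no imbalance, intent-to-treat error stays at 2.5%. These figures show sensitivity; they do not predict that the imbalance will occur. They do not invalidate the design, whose sample size and power reproduce, and they do not require redefining the endpoint. What is missing is a cheap analysis that would show whether the conclusion depends on how these patients are scored.

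**What to change.** 1. At the existing 18-month visit, record why a planned reconstruction has not been done: ipsilateral chest-wall, skin, wound or expander problem after radiation; patient choice; recurrence; unrelated illness; other. Add the reason to the by-arm summary in 12.3.2.
2. In 12.3.2, beside the exclusion analysis, pre-specify one supportive sensitivity analysis of the primary endpoint. It uses the same test and margin on all randomized patients and scores non-reconstruction for the first of those reasons as an event. Patient choice, recurrence and unrelated illness remain non-events unless a 10.1 event occurred.
3. State explicitly in 12.3.2 how a planned reconstruction not performed is scored in the primary analysis.

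Leave the primary endpoint and its decision rule unchanged. Adding a component would change the estimand and the 25% planning rate. Requiring the sensitivity analysis to agree would make it in effect co-primary, at a cost in power.

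The cost is one data field and one analysis, with no extra visit or patient. The drawback is that unblinded sites attribute the reason. A companion version counting all non-reconstruction as events, which needs no attribution, can be shown alongside, accepting that it mixes in unrelated reasons.
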